# 7.1. All Subjects Population

The all subjects population will include all subjects who signed the ICF and had any study assessment recorded in the database per the protocol.

# 7.2. Safety Population

The safety population will include all subjects who received at least 1 dose of sotorasib and have at least 1 postdose safety assessment.

# 7.3. Pharmacokinetic Population

The PK population will include all subjects who received at least 1 dose of sotorasib and have evaluable PK data. A subject may be excluded from the PK summary statistics and statistical analysis if the subject has an adverse events of vomiting that occurs at or before 2 times median time to maximum concentration or diarrhea within 24 hours of dosing.

#### 8. STATISTICAL METHODOLOGY

#### 8.1. General

Listings will be provided for all data captured in the database, with the exception of medical history. Listings will include all subjects assigned to the all subjects population and include data up to the point of study completion or discontinuation. Subjects are generally considered to have completed the study if they complete the scheduled end of study visit (rather than early termination visit). Any subject who discontinues the study will be identified accordingly in the listings. Summaries and statistical analyses will include the subjects assigned to the relevant population based on data type.

Data analysis will be performed using the SAS® statistical software package Version 9.4 (or higher if a new version is issued during the study).

Analysis Data Model (ADaM) datasets will be prepared using Clinical Data Interchange Standards Consortium (CDISC) ADaM Version 2.1 (or higher if a new version is issued during the study) and CDISC ADaM Implementation Guide Version 1.1 (or higher if a new version is issued during the study). Pinnacle 21 Enterprise Version 4.2.0 (or higher if a new

version is issued during the study) will be utilized to ensure compliance with CDISC standards.

Caution should be used when interpreting results from the statistical analyses conducted in this study because the sample size is not based on power calculations.

Where reference is made to 'valid' data, this refers to non-missing data which meet the predetermined criteria (eg, are not flagged for exclusion).

Where reference is made to 'all calculations', this includes, but is not limited to, summary statistics, statistical analyses, baseline derivation, changes from baseline, percentage changes from baseline, and any parameter derivations.

All figures will be produced on linear-linear or discrete-linear scales, as applicable, unless specifically stated otherwise.

# 8.1.1. Handling of Data Quality Issues Due to Coronavirus Disease 2019 and Related Restrictions

Due to COVID-19 and related restrictions, there is a high risk for impact to data integrity, with the recognized potential for:

- Missed visits, caused by, for example:
  - Subject unable to travel to site due to restrictions, the need to quarantine, or COVID-19 infection
  - o Subject unwilling to go to site due to fear of COVID-19 infection
  - Site postponing subject's visit due to investigator not being available (eg, if they have been dispatched to hospital handling COVID19 infections)
- Site unable to replenish supply of investigational product
- Incomplete data entry by sites due to limited resources to support study or no access to source documents or to eCRF
- Outstanding source document verification (SDV) due to sponsor or country restrictions on remote SDV, or no or limited access to site(s) for on-site visits
- Unanswered queries

At the time of the reporting of the study results, all protocol deviations due to COVID-19 or related restriction will be assessed for their severity and impact on the analyses. If needed, appropriate statistical methods will be applied as a mitigating action (eg, data might be categorized into 2 analysis groups, with and without COVID-19 and related restrictions impact); however, this will exclude any imputations of the missing values. Any mitigating actions will be agreed with Amgen Inc. in advance and identified in the CSR.

# 8.1.2. Calculation of the Summary Statistics

For continuous data the following rules will be applied:

- Missing values will not be imputed, unless specifically stated otherwise.
- Unrounded data will be used in the calculation of summary statistics.
- If the number of subjects with valid observations (n) <3, summary statistics will not be calculated, with the exception of n, minimum, and maximum.
- In general, as early termination data are not associated with any scheduled timepoint, they will be excluded from all calculations of summary statistics and statistical analyses. Exceptions may be made where justified.

For categorical data the following rules will be applied:

- For ordered categorical data (eg, AE severity), all categories between the possible minimum and maximum categories will be included, even if n = 0 for a given category.
- For non-ordered categorical data (eg, race), only those categories for which there is at least 1 subject represented will be included; unless specifically stated otherwise.
- Missing values will not be imputed, unless specifically stated otherwise. A 'missing' category will be included for any parameter for which information is missing. This will ensure that the population size totals are consistent across different parameters.

# 8.1.3. Triplicate Readings

For 12-lead electrocardiogram (ECG) data only, where triplicate readings are taken, the mean of triplicate readings will replace the separate individual triplicate readings in all calculations.

In case of incomplete triplicate readings (eg, only 2 out of 3 readings were recorded), the mean and/or medians will be calculated, as appropriate, based on the number of readings available.

#### 8.1.4. Repeat and Unscheduled Readings

For vital signs and 12-lead ECG data only, any predose value recorded in addition to the original value or a postdose value recorded within 15 minutes of the original value will be defined as a repeat value; any postdose value recorded more than 15 minutes after the original value will be defined as an unscheduled value. For all other data types (eg, laboratory parameters), any value recorded in addition to the original value will be defined as an unscheduled value.

The original value will be replaced by the last associated repeat value in all calculations.

As unscheduled values are not associated with any scheduled timepoint, they will be excluded from all calculations.

# 8.2. Subject Disposition and Population Assignment

Subject disposition and population assignment will be listed.

A summary table by treatment will be provided, based on the safety population.

# 8.3. Screening Demographics and Baseline Characteristics

The screening demographics and baseline characteristics including sex, age, race, ethnicity, height, body weight, and body mass index will be listed.

A summary table by treatment will be provided, based on the safety population.

#### 8.4. Prior and Concomitant Medication

Prior medication will be defined as medication that ends prior to dosing. Concomitant medication will be defined as medication that starts during or after dosing or starts but does not end prior to dosing.

Prior and concomitant medications will be coded using the World Health Organization Drug Dictionary (WHODrug) Global, Format B3, Version September 2020 (or later if a new version is issued during the study; see the data management plan [DMP] for more details). Prior and concomitant medications will be listed.

## 8.5. Pharmacokinetic Assessments

#### 8.5.1. Pharmacokinetic Analysis

The following PK parameters will be determined on Day 1, Day 4, and Day 7, data permitting, from plasma concentrations of sotorasib using noncompartmental methods in a validated installation of Phoenix WinNonlin (Certara, Version 8.1 or higher):

Parameter	Unitsa	Definition
AUC last	h*ng/mL	area under the plasma concentration-time curve from time zero to the last quantifiable concentration b
$AUC_{inf}$	h*ng/mL	area under the plasma concentration-time curve from time zero extrapolated to infinity c
$C_{\text{max}}$	ng/mL	maximum observed plasma concentration
$t_{\text{max}}$	h	time of the maximum observed plasma concentration
$t_{last}$	h	time of the last quantifiable plasma concentration
$t_{1/2}$	h	apparent terminal elimination half-life
CL/F	L/h	apparent total clearance
$V_z/F$	L	apparent volume of distribution during the terminal phase

<sup>a Units are based on concentration units (provided by the bioanalytical lab or preferred units for presentation of PK parameters) and dose units used in the study.

Final Version 1.0, 15Oct2021

Additional PK parameters may be determined where appropriate.

Pharmacokinetic analysis will be carried out where possible using actual dose administered (mg) and actual postdose blood sampling times. If an actual time is missing, nominal times may be used with sponsor's approval.

The parameters  $C_{max}$ ,  $t_{last}$ , and  $t_{max}$  will be obtained directly from the concentration-time profiles.

For multiple peaks, the highest postdose concentration will be reported as  $C_{max}$ . In the case that multiple peaks are of equal magnitude, the earliest  $t_{max}$  will be reported.

# 8.5.1.1. Criteria for the Calculation of Apparent Terminal Elimination Rate Constant and Half-life

The start of the terminal elimination phase for each subject will be defined by visual inspection and generally will be the first point at which there is no systematic deviation from the log-linear decline in concentrations.

The apparent terminal elimination rate constant  $(\lambda_z)$  will only be calculated when a reliable estimate can be obtained using at least 3 data points, preferably not including  $C_{max}$ , and the adjusted coefficient for determination of exponential fit (R²-adj) of the regression line is  $\geq 0.8$ . Parameters requiring  $\lambda_z$  for their calculation (eg, AUCinf  $t_{1/2}$ , CL/F, and  $V_z$ /F) will only be calculated if the R²-adj value of the regression line is  $\geq 0.8$ .

The following regression-related diagnostic PK parameters will be determined, when possible:

Parameter	Units	Definition
%AUCextrap	%	percentage of area under the concentration-time curve due to extrapolation from the last quantifiable concentration to infinity
$\lambda_z$	1/h	apparent terminal elimination rate constant
$\lambda_z$ Upper	h	end of exponential fit
$\lambda_z$ Lower	h	start of exponential fit
$\lambda_zN$	NA	number of data points included in the log-linear regression
$\lambda_z$ Span Ratio	NA	time period over which $\lambda_z$ was determined as a ratio of $t_{1/2}$
R  -adj	NA	adjusted coefficient for determination of exponential fit

Where possible, the span of time used in the determination of  $\lambda_z$  (ie, the difference between  $\lambda_z$  Upper and  $\lambda_z$  Lower) should be  $\geq 2$  half-lives. If the  $\lambda_z$  Span Ratio is  $\leq 2$ , the robustness of the  $t_{1/2}$  values will be discussed in the CSR.

<sup>c Based on the last observed quantifiable concentration

# 8.5.1.2. Criteria for Calculation and Reporting of Area Under the Concentration-time Curve

The minimum requirement for the calculation of AUC will be the inclusion of at least 3 consecutive concentrations above the lower limit of quantification (LLOQ). If there are only 3 consecutive concentrations, at least 1 should follow  $C_{max}$ .

If the extrapolated area is >20%, AUCinf (and derived parameters) will be flagged and may be excluded from the summary statistics and statistical analysis at the discretion of the sponsor or pharmacokineticist.

If AUCinf cannot be determined reliably for all subjects and/or treatments, an alternative AUC measure, such as AUC to a fixed timepoint or AUClast, may be used in the statistical analysis upon sponsor approval.

# **8.5.1.3.** Criteria for Handling Below the Limit of Quantification or Missing Concentrations for Pharmacokinetic Analysis

Plasma concentrations below the limit of quantification (BLQ) will be assigned a value of 0 before the first measurable concentration and thereafter BLQ concentrations will be treated as missing. The following rules apply to the specific situations defined below:

- If an entire concentration-time profile is BLQ, it will be excluded from PK analysis.
- Where 2 or more consecutive concentrations are BLQ at the end of a profile, the profile will be deemed to have terminated and any further quantifiable concentrations will be set to missing for the calculation of the PK parameters, unless they are considered to be a true characteristic of the profile of the drug.
- If a predose plasma concentration is missing, it will be set to 0 by default within Phoenix WinNonlin.

#### 8.5.1.4. Treatment of Outliers in Pharmacokinetic Analysis

If a value is considered to be anomalous due to being inconsistent with the expected PK profile, it may be appropriate to exclude the value from the PK analysis. However, the exclusion of any data must have strong justification and will be documented in the CSR.

Any quantifiable predose concentration value in the first treatment period will be considered anomalous and set to missing for the PK analysis. This will be set to 0 by default in Phoenix WinNonlin.

If the predose concentration is >5% of  $C_{max}$  in the second or third treatment periods, all PK concentration and parameter data will be flagged and reported but excluded from the summary statistics and statistical analysis for that period.

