## 5.7. Blinding

This is an open-label study.

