# 8.5.1.4. Treatment of Outliers in Pharmacokinetic Analysis

If a value is considered to be anomalous due to being inconsistent with the expected PK profile, it may be appropriate to exclude the value from the PK analysis. However, the exclusion of any data must have strong justification and will be documented in the CSR.

Any quantifiable predose concentration value in the first treatment period will be considered anomalous and set to missing for the PK analysis. This will be set to 0 by default in Phoenix WinNonlin.

If the predose concentration is >5% of  $C_{max}$  in the second or third treatment periods, all PK concentration and parameter data will be flagged and reported but excluded from the summary statistics and statistical analysis for that period.

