#### 8.5.2. Presentation of Pharmacokinetic Data

If the actual time of sample collection deviates from the nominal time by more than  $\pm 10\%$ , the plasma concentration will be flagged and excluded from the summary statistics.

Individual concentrations deemed to be anomalous will be flagged in the listings and excluded from the summary statistics.

For plasma concentration data the following rules will apply:

- Values that are BLQ will be set to 0 for the calculation of summary statistics.
- If the embedded BLQ value is considered anomalous within the concentration-time profile, this value will be excluded from the summary statistics.
- Where there is NR, these will be set to missing.
- If there are less than three values in the data series, only the min, max and N will be presented. The other summary statistics will be denoted as not calculated (NC). BLQ is considered a value.
- If the values are BLQ, then the arithmetic mean, arithmetic SD, median, min and max will be presented as zero, 0 and the geometric mean and geometric coefficient of variation (CV%) will be denoted as NC.
- Arithmetic mean or median values that are BLQ will be presented as 0, and the geometric mean and geometric CV% will be denoted as NC.

For PK parameters the following rule will apply:

- For the calculation of summary statistics of PK parameters, all non-reportable and NC values in a data series will be set to missing.
- AUCinfand AUClast will be set to NC if they were calculated using fewer than three concentrations, and/or three concentrations if the last is Cmax.
- Geometric mean and coefficient of variation will not be calculated for  $t_{last}$  or  $t_{max}$ .

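### The SAP lets measured concentrations be dropped from the primary Cmax and AUC because they do not fit the expected profile, without requiring an assay or handling cause, a decision time or masking

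*SAP*

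**What the plan says.** SAP 8.5.1.4 sets the rule for single concentrations: if a value is considered "anomalous due to being inconsistent with the expected PK profile, it may be appropriate to exclude the value from the PK analysis". It adds one condition: "However, the exclusion of any data must have strong justification and will be documented in the CSR." SAP 8.5.2 adds: "Individual concentrations deemed to be anomalous will be flagged in the listings and excluded from the summary statistics." SAP 8.5.3 has all concentrations listed and individual profiles plotted.

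SAP 8.5.1 takes Cmax directly from the profile as the highest postdose concentration. SAP 3 makes Cmax, AUClast and AUCinf in Periods 1 and 2 the primary endpoints. Protocol 5.7 states: "This is an open-label study." Protocol 3.2 defends this on the ground that the primary endpoints are objective.

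The same SAP section treats predose levels differently by period. For Period 1: "Any quantifiable predose concentration value in the first treatment period will be considered anomalous and set to missing for the PK analysis." The next sentence reads: "This will be set to 0 by default in Phoenix WinNonlin." No size threshold applies, and no rule excludes the profile. For later periods the trigger is a predose level above 5% of Cmax, and the consequence is worded as follows: "in the second or third treatment periods, all PK concentration and parameter data will be flagged and reported but excluded". Such a period leaves both the summaries and the model.

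**The concern.** Misfit with the expected profile is the only ground for exclusion that the general rule names. It is a judgement about the outcome data, because the value is doubted for its size and position in the curve. The text does not say what counts as strong justification, who decides, or whether the decision precedes calculation of the parameters. It also does not say whether the person deciding is unaware of treatment. By contrast, SAP 7 requires protocol deviations to be considered before database lock when populations are assigned.

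Cmax is a single observed value, so removing the peak sample replaces a subject's Cmax with the next highest concentration. Bioequivalence is concluded when the 90% CIs for Cmax and the AUCs lie within 0.80 to 1.25. If peaks are removed more readily under one treatment than the other, the ratio moves. The argument that endpoints are objective, which supports the open-label design, is weaker when the values entering them can be selected by shape.

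The secondary point is the period difference in the predose rule. Exclusion criterion 30 bars prior sotorasib, so drug is not expected before the first dose. A large level there calls for an explanation, yet the SAP attaches no validity check to it.

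**Working it through.** **Inputs.** SAP 5 and Protocol 8.1 give 132 completers, a true ratio of 0.95, limits of 0.80 and 1.25, and a log-scale RMSE of 0.472 (taken here to apply to Cmax). SAP 8.5.3 gives two one-sided tests at 0.05, that is, a 90% CI. Protocol 5.6 gives 1:1 allocation, so 66 per sequence.

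**1. The plan's own figure.** SE = 0.472 × √(2/132) = 0.0581, with 130 df. Exact power for the two one-sided tests at 0.05 each is 90.2%, and the smallest even number reaching 90% is 132. The stated sample size is reproduced.

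**2. Passing range.** Half-width = 1.657 × 0.0581 = 0.0963, and exp(−0.0963) = 0.908. The lower limit is the observed ratio × 0.908. The test passes for observed ratios between 0.80/0.908 = 0.881 and 1.25 × 0.908 = 1.135.

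**3. Weight of one exclusion.** In a balanced 2×2 crossover, each subject's log ratio has weight 1/132. If one reference Cmax falls by a fraction q, the test/reference ratio is multiplied by (1 − q)^(−1/132). A fall in a test Cmax acts the other way. The SE is held fixed throughout.

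**4. Plausible size of q.** The documents give no figure, so these are assumptions: one-compartment profiles, half-life 3 to 8 h, absorption rate constant 1 to 4 per h, and the protocol's sampling times, with the highest sample dropped.
- Smooth profile: Cmax falls 0.2 to 5%, and AUClast falls under 1%.
- With 30% log-scale noise per sample: the median Cmax fall is 12 to 15%, reaching about 37 to 41% in the worst 5% of profiles. The median AUClast fall is 2 to 5%.

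**5. Exclusions needed to change the conclusion,** using q = 13%, or 0.139 on the log scale:
- Observed 0.88: lower limit 0.799, a failure. The fall needed in one reference Cmax is 1 − (0.88/0.8808)^132 = 11.7% (with the unrounded threshold 0.88083), so one exclusion is enough.
- Observed 0.87: lower limit 0.790. 132 × ln(0.80/0.7902)/0.139 = 11.7, so 12 exclusions, all on reference profiles.
- Observed 0.86: lower limit 0.781. 132 × ln(0.80/0.7811)/0.139 = 22.7, so 23 exclusions, all on reference profiles.
- Observed 0.95: lower limit 0.863, a pass. To turn this into a failure takes 132 × ln(0.8628/0.80)/0.139 = 71.8, so 72 exclusions, all on test profiles.

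**6. Type I error at a true Cmax ratio of 1.25** (nominal 5.0%), with exclusions falling on test profiles only:
- 30% falls in 3, 7 or 13 profiles give 6.6%, 9.3% or 14.8%.
- 10% falls in 3 profiles give 5.4%.

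**7. Period 1 predose set to 0.** By the linear trapezoidal rule over the first 0.5 h, AUClast loses 0.5 × 0.5 × predose level. Under the profiles in step 4, a predose level of 5%, 20% or 50% of Cmax costs about 0.1–0.2%, 0.3–0.9% or 0.9–2.3% of AUClast. Cmax is a postdose maximum and does not change.

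**The case against.** The best defence is that the rule is hedged and transparent. Exclusion only may be appropriate, it needs strong justification, and it is reported. With every concentration listed, a reader can recompute with the values restored. Open-label conduct also does not establish that the pharmacokineticist sees treatment codes; the documents are silent. Removing peaks only lowers Cmax, so a shift toward 1 needs one-sided selection. Both AUCs must pass too, and they move far less. The 0.88 example lies within 0.001 of the passing threshold.

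Most of this stands, and it limits the size of the point. It does not remove it. Disclosure lets others audit the choice afterwards, but the prespecified CI still depends on a choice with no stated criterion. Protocol 7.1.1 already allows for investigation of unexpected results and sample reanalysis, so a route to a documented cause exists and the SAP does not use it.

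On Period 1, a reader might infer more than the text supports:
- **That zeroing conceals sample mix-ups.** It does not, because the values are listed and flagged.
- **That a sizeable predose level proves a mislabelled sample or prior exposure, and so an invalid profile.** Contamination or interference confined to that one tube would leave the postdose samples sound.
- **That the two predose rules contradict each other.** Carry-over from an earlier study dose is possible only from Period 2 onward, so some difference is reasonable.
- **That the measured value should replace zero when it is small.** This is not clearly better, since drug is not expected there.

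The term evaluable PK data in the PK population (SAP 7.3) could be used to remove a bad Period 1 profile, but it is undefined.

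**Conclusion.** The point holds and is worth correcting. SAP 8.5.1.4 allows measured values to leave the primary bioequivalence analysis on profile shape, without requiring a documented cause, a decision before parameter calculation, or masking. A reader might go further and infer that the result will be biased, or that such exclusions would commonly reverse it. The documents do not support that: they give no exclusion frequency and no evidence of one-sided selection. At the planned ratio of 0.95, a few exclusions would not change the conclusion.

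The exposure is confined to results with a CI limit close to 0.80 or 1.25, and it acts mainly through Cmax. The figures assume 132 balanced completers, an RMSE of 0.472 for Cmax, a fixed SE and, for the size of each fall, the profile model stated above. The type I error figures further assume exclusions on one treatment only and are illustrations, not predictions.

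The Period 1 rule is secondary. It is fixed rather than judgemental, cannot change Cmax and barely changes AUC. What is missing is a check on whether a profile with a large predose value is valid.

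**What to change.** **Main change, SAP 8.5.1.4.** State that the primary bioequivalence analysis uses all reported concentrations except those with a documented sample-handling or bioanalytical cause. That decision is made before PK parameters are calculated and without reference to treatment. Any analysis with shape-based exclusions is shown only as a sensitivity analysis beside the primary one. The SAP's fixed rules on BLQ values can stay as they are.

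**Secondary change.** If a Period 1 predose value exceeds 5% of that period's Cmax, check the profile's validity under Protocol 7.1.1 and report the bioequivalence result with and without that period.

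**Cost.** A few sentences in the SAP and one or two extra model runs; the sample size stays at 132 completers. The downside is that a truly erroneous value with no traceable cause remains in the primary analysis and may slightly widen the CI.
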